4.1. Protocol Deviations

- Important protocol deviations (including deviations related to study inclusion/exclusion criteria, conduct of the trial, patient management or patient assessment) will be summarised and listed.

- Important deviations which result in exclusion from the analysis population will also be summarised and listed. (Please refer to [Appendix 1: Protocol Deviation Management and Definitions for Per Protocol Population](#)).
- Protocol deviations will be tracked by the study team throughout the conduct of the study in accordance with the Protocol Deviation Management Plan.
 - Data will be reviewed prior to the unblinding of the GSK study and statistical team and freezing of the database to ensure all important deviations and deviations which may lead to exclusion from the analysis are captured and categorised on the protocol deviations dataset.
 - This dataset will be the basis for the summaries and listings of protocol deviations.
- A separate summary and listing of all inclusion/exclusion criteria deviations will also be provided. This summary will be based on data as recorded on the inclusion/exclusion page of the eCRF.

5. CONSIDERATIONS FOR DATA ANALYSES AND DATA HANDLING CONVENTIONS

[Table 1](#) provides an overview of appendices within the RAP for outlining general considerations for data analyses and data handling conventions.

Table 1 Overview of Appendices

Section	Appendix
Section 13.1	Appendix 1: Protocol Deviation Management and Definitions for Per Protocol Population
Section 13.2	Appendix 2: Time and Events
Section 13.3	Appendix 3: Assessment Windows
Section 13.4	Appendix 4: Treatment States & Phases
Section 13.5	Appendix 5: Data Display Standards & Handling Conventions 
 • Study Treatment & Sub-group Display Descriptors • Baseline Definitions & Derivations • Reporting Process & Standards
Section 13.6	Appendix 6: Derived and Transformed Data 
 • General, Study Population & Safety • Efficacy • Pharmacokinetic • Healthcare Resource Use • Pharmacogenetic
Section 13.7	Appendix 7: Premature Withdrawals & Handling of Missing Data 
 • Premature Withdrawals • Handling of Missing Data

Section	Appendix
Section 13.8	Appendix 8: Values of Potential Clinical Importance
Section 13.9	Appendix 9: Multicentre Studies
Section 13.10	Appendix 10: Examination of Covariates and Subgroups
Section 13.11	Appendix 11: Multiple Comparisons and Multiplicity
Section 13.12	Appendix 12: Model Checking and Diagnostics for Statistical Analyses

6. STUDY POPULATION ANALYSES

6.1. Overview of Planned Analyses

The study population analyses will be based on the safety population, unless otherwise specified.

Section 6 provides an overview of the planned study population analyses, with full details of data displays being presented in [Appendix 14: List of Data Displays](#).

Categorical variables will be summarised by the number and percentage of subjects, and the continuous parameters will be summarised by n, mean, median, sample standard deviation, minimum and maximum unless otherwise specified. See Section 13.5.3 for further details.

All data will be listed as presented in [Appendix 14: List of Data Displays](#).

6.2. Study Populations and Subject Disposition

A table will be produced detailing the number of subjects eligible for each of the analysis populations by treatment group (Table 1.1). The table will also show the total number of subjects screened.

The number and percentage of subjects who were randomized or entered into the trial, but deviated from the inclusion or exclusion criteria will be summarized by treatment group (Table 1.2).

A table summarising study conclusion records will be produced showing the reasons for withdrawal for any subjects not completing the study as planned (Table 1.3). For subjects who discontinue investigational product, the reasons for discontinuation will be presented in a separate table (Table 1.4). The definition of study completion is given in Section 13.7.1.

The number of subjects recruited per centre and per country will be summarised by treatment group (Table 1.5).

The reasons for screen failure will also be summarised (Table 1.6)

6.3. Protocol Deviations

The number and percentage of subjects who had deviations defined as part of the protocol deviation management plan for the study (see Section 13.1) will be summarized by treatment group (Table 1.7)

6.4. Demographic and Baseline Characteristics

Subjects' demography data (age, sex, ethnicity, weight, height, body mass index (BMI), respiratory rate, G6PD enzyme activity and G6PD enzyme activity as a percentage of the site's median) will be summarised for the safety population (Table 1.8).

Summaries of race and racial combinations (Table 1.9) and race and racial combination details (Table 1.10) will be produced.

Malaria signs and symptoms (Table 1.14), splenomegaly status at baseline (Table 1.19) and previous episodes of malaria (Table 1.20) will be summarised by treatment group.

The eCRF captured the System Organ Class of current and past medical conditions, as well as preferred terms for current and past medical conditions of particular interest. Therefore, 4 summaries will be produced:

- Summary of Current Medical Conditions by Body System (Table 1.15)
- Summary of Past Medical Conditions by Body System (Table 1.16)
- Summary of Current Specific Medical Conditions (Table 1.17)
- Summary of Past Specific Medical Conditions (Table 1.18)

In addition to the G6PD enzyme activity test, which was used to assess whether subjects were eligible to enter the study, a point of care test may also have been administered, which classified subjects as G6PD normal or G6PD deficient (Table 1.22). The results of the point of care test will be summarised (n, %) versus the enzyme activity test for all subjects screened in the study, where G6PD enzyme activity is classified as <40% of median, 40% to <70% of median, and >=70% of median. This display will not be presented by treatment group.

Baseline efficacy data (e.g., asexual parasite counts and parasite gametocyte counts) will not be summarised and listed separately but will be included in efficacy summaries by assessment.

6.5. Prior and Concomitant Medications

Prior and concurrent medications will be tabulated (Table 1.11 and Table 1.12). Percentages will be calculated out of the number of subjects in the safety population. See Section 13.6.2 for definitions of prior and concomitant medications.

Paracetamol usage will be summarised separately (Table 1.13).

6.6. Exposure and Treatment Compliance

Compliance (defined in Section 13.6.2) will be summarised split by in clinic and outpatient dosing (Table 1.21). For in clinic compliance, the number of compliant doses of CQ and whether subjects were compliant with TQ/TQ placebo and each dose of in clinic PQ/PQ placebo will be summarised (n, %). For outpatient compliance, the number of doses taken will be summarised classified into 11 or fewer doses, 12 or more doses. Compliance determined using Day 8, Day 15, Day 8 or Day 15, Day 8 and Day 15 carboxyPQ PK samples will also be summarised in the table. A summary of subjects meeting the pill count and PK compliance criteria, and also the number of subjects meeting the pill count or PK compliance criteria will additionally be provided in the table.

7. PRIMARY STATISTICAL ANALYSES

7.1. Safety Analyses

7.1.1. Overview of Planned Safety Analyses

The primary safety analyses will be based on safety population, unless otherwise specified.

Full details of data displays are presented in [Appendix 14: List of Data Displays](#).

7.1.2. Planned Safety Statistical Analyses

Primary Statistical Analyses
Endpoint(s)

 Occurrence of clinically relevant haemolysis in all subjects. See Section 13.6.3 for derivation of clinically relevant haemolysis.
Model Specification

 No formal statistical analyses will be performed as the incidence of clinically relevant haemolysis is expected to be low. 95% confidence intervals for the proportion of subjects (\hat{p}) with clinically relevant haemolysis in each treatment group (i, j) will be based in the Wilson score: $\left(\hat{p}_i + z_{\alpha/2}^2 / 2n_i \pm z_{\alpha/2} \sqrt{(\hat{p}_i(1 - \hat{p}_i) + z_{\alpha/2}^2 / 4n_i) / n_i} \right) / 1 + z_{\alpha/2}^2 / n_i$ This can be obtained in SAS using the BINOMIAL option in PROC FREQ. The Newcombe method based on the Wilson score will be used to calculate the 95% confidence interval for the difference in proportion ($\hat{p}_i - \hat{p}_j$) (Newcombe, 1998): $\text{lower limit} = (\hat{p}_i - \hat{p}_j) - \sqrt{(\hat{p}_i - L_i)^2 + (U_j - \hat{p}_j)^2}$ $\text{upper limit} = (\hat{p}_i - \hat{p}_j) + \sqrt{(U_i - \hat{p}_i)^2 + (\hat{p}_j - L_j)^2}$ where U and L represent the upper and lower limit respectively of the corresponding

Primary Statistical Analyses

proportion. This can be obtained in SAS using the RISKDIFF option with (CL=(NEWCOMBE)) in PROC FREQ.

Results Presentation

 Table 3.1, Figure 3.1: The proportion of subjects with clinically relevant haemolysis in each treatment group will be presented together with a confidence interval based on the Wilson score The difference between treatment groups in the proportion of subjects with clinically relevant haemolysis in each treatment group will be presented together with a confidence interval based on the Newcombe method (tables only) Due to the low number of G6PD deficient females expected, they will be included in the primary analysis but their data will be listed separately.

Sensitivity and Supportive Statistical Analyses

 To assess the impact of missing data, a sensitivity analysis will be performed using imputed data where data is missing, as described in Section 13.7.2.3 and the methodology detailed above (Table 3.2).

Further safety analyses are described in Section 8.2.

8. SECONDARY STATISTICAL ANALYSES

8.1. Efficacy Analyses

8.1.1. Overview of Planned Efficacy Analyses

The secondary efficacy analyses will be based on mITT population, unless otherwise specified.

Details of data displays are presented in [Appendix 14: List of Data Displays](#).

8.1.2. Planned Efficacy Statistical Analyses

Secondary Statistical Analyses
Endpoint(s)

 Relapse-free efficacy six months post-dosing Relapse-free efficacy four months post-dosing See Section 13.6.4 for derivations including censoring.
Model Specification

 Estimates for the relapse-free efficacy rate and time to relapse will be determined for each treatment group using the Kaplan-Meier method. Cox Proportional Hazards model with region and treatment as covariates will provide the hazard ratio mITT population

Secondary Statistical Analyses
Model Checking & Diagnostics

 Refer to Appendix 12: Model Checking and Diagnostics for Statistical Analyses.
Model Results Presentation

 Summary of the proportion of subjects with relapse-free efficacy by treatment group as n (%), including the sub-reasons for why subjects are not considered relapse-free defined in Section 13.6.4 (Table 2.5 for 6 months, Table 2.7 for 4 months). Note only the sub-reasons that apply to the population being displayed will be included. Analysis tables (Table 2.9 for 6 months, Table 2.11 for 4 months) will show: 
 Number of subjects with an observed relapse and numbers of subjects censored (censored prior to 6/4 months, and censored relapse-free at 6/4 months) Kaplan-Meier estimate and 95% confidence intervals of the relapse-free efficacy rate at 6/4 months for each treatment Kaplan-Meier quartile estimates and 95% confidence intervals of time to relapse Hazard ratio of TQ+CQ vs PQ+CQ over the first 6/4 months from Cox Proportional Hazards model 95% CI Kaplan-Meier survival curves will also be produced for 6 months (Figure 2.1).

Sensitivity and Supportive Statistical Analyses
1. Per Protocol population – Relapse free efficacy at 6 months and 4 months

 Summary of the proportion of subjects with relapse-free efficacy by treatment group as n (%), including the sub-reasons for why subjects are not considered relapse-free defined in Section 13.6.4 (Table 2.6 for 6 months, Table 2.8 for 4 months). Note only the sub-reasons that apply to the population being displayed will be included. Analysis tables (Table 2.10 for 6 months, Table 2.12 for 4 months) will show: 
 Number of subjects with an observed relapse and numbers of subjects censored (censored prior to 6/4 months, and censored relapse-free at 6 months) Kaplan-Meier estimate and 95% confidence intervals of the relapse-free efficacy rate at 6/4 months for each treatment Kaplan-Meier quartile estimates and 95% confidence intervals of time to relapse Hazard ratio of TQ+CQ vs PQ+CQ over the first 6/4 months from Cox Proportional Hazards model 95% CI Kaplan-Meier survival curves will also be produced for 6 months (Figure 2.2).
2. Logistic Regression Model – 6 months and 4 months

 6 months: Table 2.13, 4 months: Table 2.14 Logistic regression model with region and treatment as covariates. Response variable = relapse free (confirmed at 6 (or 4) months) vs relapse (confirmed relapse at or prior to 6 (or 4) months). Subjects who are censored prior to 6 (or 4) months will be excluded from the analysis. mITT only Present the number and percentage of subjects considered relapse free, the adjusted odds ratio of TQ+CQ vs PQ+CQ and 95% CI for the odds ratio
3. Missing=Failure analysis - 6 months and 4 months

 See Section 13.6.4 for derivation of missing=failure dataset Logistic regression with region and treatment as covariates

Sensitivity and Supportive Statistical Analyses

 • mITT only • Presentation of results (6 months: Table 2.15, 4 months: Table 2.16): 
 • Number and percentage of subjects considered relapse free • Adjusted odds ratio of TQ+CQ vs PQ+CQ and 95% CI
4. Missing on or after Day 29 = Failure analysis – 6 months

 • See Section 13.6.4 for derivation of missing=failure dataset • Logistic regression with region and treatment as covariates • mITT only • Presentation of results (Table 2.17): 
 • Number and percentage of subjects considered relapse free • Adjusted odds ratio of TQ+CQ vs PQ+CQ and 95% CI
5. By genetic classification - 6 months and 4 months

 • Repeat primary analysis censoring subjects with homologous infections (6 months: Table 2.18, 4 months: Table 2.20); and censoring subjects with heterologous infections (6 months: Table 2.19, 4 months: Table 2.21) present: 
 • Number of subjects with an observed relapse and numbers of subjects censored • Kaplan-Meier estimate and 95% confidence intervals of the relapse-free efficacy rate for each treatment • Kaplan-Meier estimate and 95% confidence intervals of the relapse-free efficacy rate at 6/4 months for each treatment • Kaplan-Meier quartile estimates and 95% confidence intervals of time to relapse • Kaplan-Meier survival curves (6 months only: Figure 2.3, Figure 2.4)
6. Covariate and Interaction Testing

 • The significance of region and the treatment*region interaction will be tested in the Cox Proportional Hazards model. The primary model will be fitted with region and treatment as covariates, and another model will be fitted with the additional treatment*region interaction. • The significance of the chloroquine supply date category (as described in Section 13.10.1) and the treatment*chloroquine supply date category will also be fitted on top of the core model. The covariate will be fitted first on top of the core model, and then the treatment*covariate interaction will be fitted additionally. • mITT only • The degrees of freedom, Wald chi-square and p-values will be presented (Table 2.22) • If the treatment*region interaction is significant at the 10% level, analyses split by region will be performed.
7. By Chloroquine Supply Date Category

 • Repeat primary analysis by chloroquine supply date category (as described in Section 13.10.1) (6 months: Table 2.23, 4 months: Table 2.24), regardless of whether the interaction with treatment tested in Table 2.20 is significant or not.

Secondary Statistical Analyses
Endpoint(s)

 • Time to relapse • Time to parasite clearance • Time to fever clearance

Secondary Statistical Analyses

 Time to gametocyte clearance See Section 13.6.4 for derivations including censoring.
Model Specification

 mITT population Estimates for time to endpoint will be determined for each treatment group using the Kaplan-Meier method. Cox Proportional Hazards model with region and treatment as covariates
Model Checking & Diagnostics

 Refer to Appendix 12: Model Checking and Diagnostics for Statistical Analyses.
Model Results Presentation

 Time to relapse: this is covered in Table 2.9 Time to clearance endpoints: Table 2.25 to Table 2.27: 
 Number of subjects with the endpoint and number censored Estimates for time to the endpoint: 1st quartile, median, 3rd quartile and associated 95% confidence intervals Hazard ratio (TQ+CQ vs PQ+CQ) and 95% confidence interval

Secondary Statistical Analyses
Endpoint(s)

 Recrudescence - see Section 13.6.4 for derivations including censoring
Model Specification

 No statistical model will be constructed; descriptive statistics only 95% Wilson confidence intervals for the rate of recrudescence in each treatment group and treatment difference in the rate mITT population
Model Results Presentation

 Summary table showing the number of subjects with recrudescence or censored, rate of recrudescence and 95% CI for each treatment group, plus treatment difference and 95% CI (Table 2.29).

Secondary Statistical Analyses
Endpoint(s)

 Early failures See Section 13.6.4 for derivation
Model Specification

 No statistical model will be constructed; descriptive statistics only mITT population
Model Results Presentation

 Summary table (n and %) showing the proportion of subjects in each treatment group (Table 2.30): 
 Considered early failures Early failures who fail to demonstrate initial clearance

Secondary Statistical Analyses

 • Early failures who demonstrate initial clearance • Early failures who demonstrate initial clearance with genetically homologous infections • Early failures who demonstrate initial clearance with genetically heterologous infections • Early failures who demonstrate initial clearance with missing parasite genetics 
 • Listing of subjects considered early failures, together with their CQ and desethylCQ concentrations from the PK draw closest to the study day of recrudescence, and whether the infection is determined genetically homologous or heterologous (Listing 29).

Secondary Statistical Analyses
Endpoint(s)

 • Genetic classification by PCR of relapse infections occurring on or after Study Day 33 • See Section 13.6.4 for derivation of a relapse
Model Specification

 • No statistical model will be constructed; descriptive statistics only • mITT population
Model Results Presentation

 • Summary table (n and %) (Table 2.31) showing the proportion of subjects in each treatment group with P. vivax relapse infections classified as genetically heterologous or homologous • n will be the number of subjects with a relapse occurring on or after Study Day 33 • Bar chart of the percentage of subjects on each treatment arm with genetically heterologous or homologous infections, with 95% Wilson confidence intervals (Figure 2.5)

Secondary Statistical Analyses
Endpoint(s)

 Effect of CYP2D6 metabolism on relapse-free efficacy six months post-dosing within the treatment arms
Model Specification

 mITT population Logistic regression model adjusting for region and derived CYP2D6 metabolizer class within treatment arm (models fitted separately for each treatment arm) One-sided test at the 5% significance level (given published data indicating reduced CYP2D6 metabolism decreases PQ efficacy) Table 2.33: Poor Metaboliser (PM) and Intermediate Metaboliser (IM) vs Extensive Metaboliser (EM) and Ultra Metaboliser (UM) combined (PM vs EM+UM, IM vs EM+UM) Table 2.34: Intermediate Metaboliser vs Extensive Metaboliser (IM vs EM) (Rationale: the number of PMs and the number of UMs are expected to be small)
Model Results Presentation

 Number and percentage of subjects relapse free in each metaboliser class within each treatment arm Adjusted odds ratio, 90% CI and p-value

Secondary Statistical Analyses
Endpoint(s)

 Effect of qualitative CYP2D6 Activity Score (AS) on relapse-free efficacy six months post-dosing within the treatment arms
Model Specification

 mITT population Logistic regression model adjusting for region and qualitative CYP2D6 AS within treatment arm (models fitted separately for each treatment arm)
Model Results Presentation

 Table 2.35: degrees of freedom, wald chi-square and p-value of the type III effect of AS in the model

Additional Efficacy Summaries

 P. vivax asexual parasite counts (Table 2.1), mITT population: 
 Summary statistics (n, median, Q1, Q3, min and max) at each timepoint Other malarial asexual parasite counts (Table 2.2), P. vivax gametocyte counts (Table 2.3), other malaria gametocyte counts (Table 2.4), mITT population: 
 Summary statistics (n, median, Q1, Q3, min and max) at each timepoint Summary of subjects with P. vivax gametocyte emergence post baseline (n, %) (Table 2.28) Summary of subjects with P. falciparum asexual parasite emergence post baseline (n, %) (Table 2.32)

Efficacy Listings

 Efficacy data will be listed as presented in Appendix 14: List of Data Displays

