8.3.4.3. Secondary Efficacy Analyses

The proportion of patients with relapse-free efficacy at four months and six months will be summarized by treatment group and analyzed using Kaplan-Meier methodology where subjects with missing data are censored, and by separate Fisher's Exact analyses where subjects are classified as a treatment failure if they do not have a six month result or took any drug with activity against *P.vivax*.

The time to relapse, parasite clearance time, fever clearance time and time to gametocyte clearance will be compared using the Kaplan-Meier method and summarized and listed by treatment group.

The incidence rates of genetically homologous and genetically heterologous *P. vivax* infection determined by PCR as well as recrudescence, defined as any *P. vivax* parasitemia occurring on or before Day 32 (*i.e.*, blood stage treatment failure), will be summarized and listed by treatment group.

Subjects will be assessed for clearance times against the following definitions:

Parasite Clearance Time (PCT): Time needed to clear asexual parasite from the blood defined as parasite numbers falling below the limit of detection in the thick blood smear and remaining undetectable 6-12 hours later.

Fever Clearance Time (FCT): Time from first dose of treatment to the time when body temperature falls to normal and remains normal for at least 48 hours.

Gametocyte Clearance Time (GCT): Time from first dose until the first slide that was gametocyte negative and remained so at the next slide reading. Subjects with no gametocytes at baseline will be censored, with a time to clearance of zero.

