2.2. Study Objective(s) and Endpoint(s)

Objectives	Endpoints
Primary Objectives	Primary Endpoints

 To investigate the occurrence of clinically relevant haemolysis in adult subjects with P. vivax. 	
 Occurrence of clinically relevant haemolysis in all subjects; defined as, a decrease in haemoglobin of $\geq 30\%$ or >30 g/L (>3 g/dL) from baseline; or, an overall drop in haemoglobin below 60 g/L (6.0 g/dL).
Secondary Objectives	Second Endpoints

 To compare the clinical and parasitological efficacy, safety and tolerability of tafenoquine to primaquine as a radical cure for 	
 Relapse-free efficacy six months post-dosing Relapse-free efficacy four months post-dosing Time to relapse

Objectives	Endpoints

adult subjects with P. vivax malaria when co-administered with chloroquine.
	
 • Parasite clearance time • Fever clearance time • Gametocyte clearance time • Recrudescence, defined as any P. vivax parasitemia occurring on or before Day 32 (i.e. blood stage treatment failure). • Incidence of genetically homologous and genetically heterologous P. vivax infections (determined by PCR) • Safety evaluation of data from clinical laboratory tests, urinalysis, spontaneous/elicited adverse event reporting, ECGs and vital signs in all subjects who received at least one dose of study medication. • Incidence of P. falciparum malaria • Ophthalmic assessments

 • To characterize the socioeconomic impact of P. vivax relapse. 	
 • Characterization of healthcare resource use and socio-economic impact of P. vivax relapses and adverse events caused by treatment to prevent P. vivax relapses, especially haemolytic anemia.

 • To evaluate the pharmacokinetics of tafenoquine in the treatment of adult subjects with P. vivax malaria. 	
 • Population PK parameters for tafenoquine including but not limited to oral clearance (CL/F) and volume of distribution (V/F)

 • To characterize the pharmacokinetic/ pharmacodynamic relationship in this study population. 	
 • PK and selected PD endpoints (e.g. relapse-free efficacy, change in methaemoglobin) if appropriate

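### RAP Table 2.31 shows the genetic mix among relapsers, not the incidence of homologous and heterologous infection by arm that the protocol names, and the denominator of Figure 2.5 is not stated

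*Supplement*

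**What the plan says.** The RAP (section 2.2) lists the secondary endpoint as "Incidence of genetically homologous and genetically heterologous" *P. vivax* infections, determined by PCR. Protocol Amendment 5, section 8.3.4.3, begins its analysis sentence with "The incidence rates of genetically homologous and genetically heterologous" infection and says these rates, together with recrudescence, will be summarised and listed by treatment group.

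RAP Amendment 1, section 8.1.2, delivers the part of this endpoint from Day 33 onwards in Table 2.31. The table is descriptive, is run on the mITT population, and counts "relapse infections classified as genetically heterologous or homologous". Its size is fixed by "n will be the number of subjects with a relapse occurring on or after Study Day 33". The accompanying Figure 2.5 is a "Bar chart of the percentage of subjects on each treatment arm with genetically heterologous or homologous infections, with 95% Wilson confidence intervals", with no denominator given.

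Three other parts of the RAP bear on the point:

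- Table 2.30 (early failures, up to Day 32) gives proportions of subjects in each treatment group and has a category for missing parasite genetics.
- Tables 2.18 to 2.21 and Figures 2.3 and 2.4 repeat the relapse analysis on mITT with one infection type censored at a time. Their output includes the "Kaplan-Meier estimate and 95% confidence intervals of the relapse-free efficacy rate at 6/4 months for each treatment".
- Section 2.1 lists departures from the protocol analysis. A change of denominator for this endpoint is not among them.

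**The concern.** An incidence by arm has the subjects in that arm as its base. Table 2.31 uses only those who relapsed on or after Day 33. Relapse is itself a treatment outcome, so comparing percentages within relapsers is no longer a comparison of randomised groups. If tafenoquine and primaquine differ in how often homologous recurrences occur, but the mix of types among recurrences is similar, the table shows two equal percentages. If the mix differs, the percentages can rank the arms in the opposite order to their incidences.

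The wording adds to the risk. Both displays speak of subjects in each treatment group or arm, so a reader would take the percentages as incidences. Any Wilson intervals built on relapsers would describe the mix, not the endpoint.

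**Working it through.** **Reading n as the denominator.** RAP section 13.5.3 lists n separately from the frequency for categorical displays. In Table 2.31, n is therefore naturally the base of the percentage and not the count of events. The plan states no numerical figure for this endpoint, so there is none to reproduce.

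**Notation, per arm.** N = mITT subjects, R = subjects with a relapse on or after Day 33, H = those whose relapse is homologous.

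- Table 2.31 percentage: H/R
- Incidence: H/N = (R/N) × (H/R)

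The table drops the factor R/N, which is the part that carries the difference in relapse between arms.

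**Inputs from the documents.** Planned arms are 200 and 100 (protocol 8.2.1). The number randomised is 251 (meta-analysis plan, section 3), or about 167 and 84 at exactly 2:1. The only primaquine plus chloroquine relapse count given is 12/40 = 30%, among six-month completers in Part 1 of the sister study (meta-analysis plan 9.3).

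**Assumptions.** Primaquine relapse of 10% to 30%, tafenoquine relapse half or twice that, and a homologous share of 50% unless stated. All relapse and homologous counts below are illustrative. Intervals are Wilson 95%, and differences use the Newcombe method.

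| N (TQ, PQ) | R (TQ, PQ) | H (TQ, PQ) | H/R, TQ v PQ | H/N, TQ v PQ |
|---|---|---|---|---|
| 200, 100 | 40, 10 | 20, 5 | 50.0% (35.2–64.8) v 50.0% (23.7–76.3) | 10.0% (6.6–14.9) v 5.0% (2.2–11.2) |
| 200, 100 | 20, 20 | 10, 10 | 50.0% (29.9–70.1) in both | 5.0% (2.7–9.0) v 10.0% (5.5–17.4) |
| 200, 100 | 30, 30 | 15, 15 | 50.0% (33.2–66.8) in both | 7.5% (4.6–12.0) v 15.0% (9.3–23.3) |
| 167, 84 | 24, 24 | 12, 12 | 50.0% (31.4–68.6) in both | 7.2% (4.2–12.1) v 14.3% (8.4–23.3) |
| 167, 84 | 32, 8 | 16, 4 | 50.0% (33.6–66.4) v 50.0% (21.5–78.5) | 9.6% (6.0–15.0) v 4.8% (1.9–11.6) |

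In the third row the difference in incidence is −7.5 points (−16.3 to −0.2), while the difference in the table's percentages is zero. Homologous shares of 30% or 70% give the same pattern: equal percentages among relapsers and a twofold ratio of incidence.

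**Reversal.** Take 15 homologous of 20 relapsers in an arm of 200, against 20 of 50 in an arm of 100. Table 2.31 would read 75.0% against 40.0%. Incidence is 15/200 = 7.5% against 20/100 = 20.0%.

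**Missing genetics.** If a fraction m of relapsers is untyped but stays in n, and untyped relapses have the same mix as typed ones, each share is multiplied by (1 − m). With an assumed m of 20%, a true 50% shows as 40%, and the two types add to 80%. The documents give no missing rate. The shell for Table 2.31 is not in the supplement, so whether it carries a missing row is unknown.

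**The case against.** The strongest reply is that the RAP already relates type-specific infection to all treated subjects. Tables 2.18 to 2.21 do so on mITT with confidence intervals, and Table 2.30 does so for early failures. A reader might infer that the incidence by type is nowhere obtainable. The documents do not support that. In every scenario above the Kaplan-Meier rates would show the difference, and H/N can be recovered by dividing Table 2.31 counts by the arm's mITT N.

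That answer stands but does not settle the point. The Kaplan-Meier tables sit among the sensitivity and supportive analyses of relapse-free efficacy. The relapse definition they inherit (section 13.6.4) takes in events before Day 33 and places non-clearance at day 0. Censoring the other type gives a net rate, not the crude proportion who had that type. Hand division also leaves any relapser-based intervals attached to the wrong quantity.

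Two further inferences go too far. The rule on n follows the Table 2.31 bullet, so Figure 2.5 cannot be said to use relapsers; its denominator is simply not stated. Nor can a particular bias from missing genetics be claimed, because both the rate and the shell are unknown.

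It is also fair that this is one descriptive secondary display in a study that tests no hypotheses, that the protocol names no explicit denominator, and that the mix among recurrences is informative in itself.

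**Conclusion.** The point holds for Table 2.31. It is the descriptive display for an endpoint named as an incidence by treatment group, and it reports the genetic mix within a post-randomisation subset. The departure is not declared in RAP section 2.1. For Figure 2.5 the finding is an ambiguity: the wording suggests all subjects in the arm, and nothing confirms it.

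The possible distortion is a full twofold difference hidden behind equal percentages, or a reversed order. Which of these occurs, if either, depends on relapse counts and genetic mix that are assumed here. The identity H/N = (R/N) × (H/R) needs no such assumption.

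The consequence is limited. No primary conclusion or test rests on this table, and supportive analyses on mITT exist. It is worth correcting because a named secondary endpoint should be estimated by its own display.

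**What to change.** In Table 2.31 and Figure 2.5, report homologous, heterologous and missing-genetics infections as n/N, with N the mITT subjects in each arm, and give Wilson 95% intervals. Label both displays as covering Day 33 onwards and refer to Table 2.30 for events up to Day 32, since the protocol endpoint has no Day 33 limit. Keep the homologous/heterologous split among relapsers with a genetic result as a secondary row, labelled as the mix among relapses. State the denominator of Figure 2.5 explicitly.

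The cost is one line in RAP section 8.1.2 and edits to two shells, with no new data. The drawback is that crude n/N counts a subject lost before Day 180 without a recorded relapse as event-free. A footnote should say so and direct the reader to Tables 2.18 to 2.21, which handle such losses by censoring. If the sponsor prefers to keep the relapser denominator, section 2.1 should list it as a departure and the table title should say what is shown.
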